**SAMPLE SIZE DETERMINATION:**

The required sample size is 82 participants based on the below specifications that have received at least 1 dose of posoleucel or PBO.

The sample size was determined based on the following specifications:

1. Superiority study comparing posoleucel plus SoC to placebo plus SoC
2. Primary endpoint is success or failure based on clearance of ADV viremia at Day 29 visit of the Primary Study Period
3. Allocation (posoleucel:placebo) is 1:1
4. Chi-square test
5. Two-sided alpha = 0.05
6. True success rate (defined as clearance of virus) for posoleucel = 0.55
7. True success rate (defined as clearance of virus) for placebo = 0.25
8. Power = 80%

A SSRE and futility analysis will be performed after approximately 40 participants have completed Day 29 of the Primary Study Period. Details of the SSRE and futility analysis will be provided in the SSRE Plan prior to conducting the interim analyses.

---

**SITES:** Approximately 50 clinical sites in the United States, Canada, and Europe.

---

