The durability of response in viremia will be evaluated after the Day 29 timepoint throughout the remainder of the study. This will be accomplished at the protocol-specified evaluations (including viral load determinations at the central laboratory) at Weeks 5, 6, 10, 16, and 24, and will be addressed specifically by the following two secondary efficacy endpoints: a) To determine the percent of participants who develop target organ AdV disease (eg, lower tract respiratory disease documented radiographically, AdV-associated hemorrhagic cystitis, severe hepatitis) or whose target organ disease progresses during the study, and b) To evaluate the proportion of participants who have recurrence of viremia ( $\geq 10,000$  copies/mL AdV DNA) and/or target organ disease during the study (among participants who had clearance of AdV viremia).

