## 10 STATISTICAL CONSIDERATIONS

### 10.1 Sample Size Determination

The required sample size is 82 participants based on the below specifications that have received at least 1 dose of posoleucel or PBO.

The sample size was determined based on the following specifications:

1. Superiority study comparing posoleucel plus SoC to placebo plus SoC
2. Primary endpoint is success or failure based on clearance of ADV viremia at Day 29 of the Primary Study Period
3. Allocation (posoleucel:placebo) is █
4. Chi-square test
5. Two-sided alpha = 0.05
6. True success rate (defined as clearance of virus) for posoleucel = 0.55
7. True success rate (defined as clearance of virus) for placebo = 0.25
8. Power = 80%

A SSRE and futility analysis will be performed after approximately 40 participants have completed Day 29 of the Primary Study Period. Details of the SSRE and futility analysis will be provided in the SSRE Plan prior to conducting the interim analyses.

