#### 10.3.1.1 Primary Efficacy Endpoint Analysis

The primary efficacy endpoint, undetectable viremia (less than LLOQ) at Day 29 of the Primary Study Period, will be summarized by treatment group using the count and percentage, together with an exact (Clopper-Pearson) 95% confidence interval for the true percentage.

The null hypothesis is that the true percentage for posoleucel plus SoC is less than or equal to the true percentage for placebo plus SoC, and the alternative hypothesis is that it is greater. This endpoint will be analyzed using logistic regression. The model will include a term for treatment and the following covariates: level of viremia at Baseline ( $\geq 10,000$  copies/mL or  $< 10,000$

copies/mL AdV DNA), age ( $\geq 12$  years or  $< 12$  years) and absolute lymphocyte count at Baseline. The null hypothesis will be tested using a one-sided test of the effect of treatment at the 0.025 significance level. Missing data imputation will be described in the SAP.

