#### 10.3.1.3 Other Secondary Efficacy Endpoint Analyses

Following the key secondary analysis, progression from viremia to target organ disease and progression of target organ disease will be analyzed as separate subgroups in a step-down manner. If any participants cross over prior to Day 29, they will be considered as having had progression, because the necessary condition for cross-over is that the participant progressed to active target organ disease (for participants without target organ disease at screening) or experienced progression of target organ disease (for participants with target organ disease at screening).

The AAUC for plasma AdV viremia ( $\log_{10}$  copies/mL AdV DNA), as assayed by qPCR, through Day 29 of the Primary Study Period will be summarized by treatment group using descriptive statistics (number of non-missing observations, mean, median, standard deviation, minimum, and maximum). The null hypothesis for this endpoint is that the true mean for posoleucel is greater than or equal to the true mean for placebo, and the alternative hypothesis is that it is less. The null hypothesis will be tested using a one-sided, two-sample t-test with a 0.025 significance level.

The following secondary efficacy endpoints will each be analyzed in the same manner as the primary efficacy endpoint: achieving AdV viremia  $< 400$  copies/mL AdV DNA at Day 29 of the Primary Study Period and AdV disease recurrence during the study among participants who had clearance of AdV viremia (prior to any cross-over).

The Kaplan-Meier estimated median time to resolution of AdV viremia will be presented for each treatment group, together with the 95% confidence interval for the true median. The number and percentage of censored and uncensored participants will be presented by treatment group. The null hypothesis for this endpoint is that the true distributions of time to resolution of AdV viremia are equal for posoleucel and placebo, and the alternative hypothesis is that the true distributions are different, with the time to resolution of AdV viremia being less for posoleucel. The null hypothesis will be tested using a one-sided log-rank test with a 0.025 significance level.

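### Protocol Section 10.3.1.3 plans a formal test of recurrence only among participants who cleared, a subset formed by response to treatment, so it is not a randomized comparison

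*Protocol*

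**What the plan says.** Protocol Section 10.3.1.3 names two secondary endpoints that are to be handled as the primary endpoint is. One of them is "AdV disease recurrence during the study among participants who had clearance of AdV viremia (prior to any cross-over". Section 10.3.1.1 defines that handling: logistic regression on treatment, baseline viremia (above or below 10,000 copies/mL), age (above or below 12 years) and baseline absolute lymphocyte count. The test is specified as "The null hypothesis will be tested using a one-sided test of the effect of treatment at the 0.025 significance level". The null is that the posoleucel percentage is no higher than the placebo percentage, "and the alternative hypothesis is that it is greater". Section 10.3.1 adds that all efficacy endpoints are formally compared between the randomized groups. It applies the estimand framework and the sequential control of type 1 error only to the primary and key secondary endpoints.

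Section 5.4 states "The durability of response in viremia will be evaluated after the Day 29 timepoint throughout the remainder of the study". It names two endpoints for this purpose: recurrence among clearers, and target organ disease developing or progressing during the study. The same section describes the risk of recurrence after clearance only as low and gives no figure.

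The SAP (Section 1) says that the study was terminated for futility and that only the primary efficacy endpoint and selected safety endpoints will be analysed. SAP Sections 3.1 and 3.4 confirm that there are no hypothesis tests and no secondary efficacy endpoints.

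**The concern.** The denominator for recurrence is defined by clearance, which is the outcome posoleucel is meant to change. If posoleucel works, its clearers include participants who would not have cleared on placebo, and the placebo clearers have no counterpart to them. If those extra clearers have a different underlying risk of recurrence, the arms will differ even when treatment does nothing to recurrence. A one-sided p-value from such a comparison would be read as evidence on durability when it mixes a treatment effect with selection.

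The model covariates may reduce this bias but cannot be relied on to remove it: two are dichotomized, and steroid exposure and cidofovir use, for example, are not in the model. The protocol gives no estimand or sensitivity analysis for this endpoint.

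There is also a wording fault. For clearance, a greater percentage on posoleucel is favourable. Carried over literally to recurrence, the same alternative would count more recurrence on posoleucel as success. Section 10.3.1.3 writes out a reversed alternative for the viremia AAUC but none for recurrence.

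**Working it through.** **Inputs from the protocol.** "True success rate (defined as clearance of virus) for posoleucel = 0.55"; "True success rate (defined as clearance of virus) for placebo = 0.25"; "Two-sided alpha = 0.05"; 80% power; chi-square test (Section 10.1). "Allocation (posoleucel:placebo) is 1:1" (synopsis).

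**The plan's own figure.** With pooled variance and a mean rate of 0.40, n per arm = [1.960 × √(2 × 0.40 × 0.60) + 0.842 × √(0.55 × 0.45 + 0.25 × 0.75)]² / 0.30² = (1.358 + 0.555)² / 0.09 ≈ 40.7, so 41 per arm and 82 in total. This reproduces, with power 80.3%. A one-sided 0.025 test gives the same 41.

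**Expected clearers.** 41 × 0.55 = 22.6 on posoleucel and 41 × 0.25 = 10.3 on placebo, taking the Day 29 rates as a guide to the denominator.

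**Assumptions.** Treatment never prevents clearance. Then 25% of participants clear on either arm, 30% clear only on posoleucel, and 45% clear on neither. Treatment has no effect on recurrence in those who clear either way. Let a be the recurrence risk in the 25% and b the risk in the 30%. The documents supply neither value, so both are assumed.

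- Recurrence among clearers: posoleucel (0.25a + 0.30b) / 0.55; placebo a.
- Cleared without recurrence, all participants: posoleucel 0.25(1 − a) + 0.30(1 − b); placebo 0.25(1 − a).

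With a = 10%:

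| b | Recurrence among clearers, posoleucel vs placebo | Odds ratio | Cleared without recurrence, all participants | Power at 41 per arm |
|---|---|---|---|---|
| 10% | 10.0% vs 10.0% | 1.00 | 49.5% vs 22.5% | 73% |
| 20% | 15.5% vs 10.0% | 1.65 | 46.5% vs 22.5% | 63% |
| 30% | 20.9% vs 10.0% | 2.38 | 43.5% vs 22.5% | 53% |
| 40% | 26.4% vs 10.0% | 3.22 | 40.5% vs 22.5% | 42% |

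Worked row, b = 30%: (0.025 + 0.090) / 0.55 = 0.209; 0.225 + 0.210 = 0.435.

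**Other values.** With b = 40%, the odds ratio is 6.0 at a = 5% and 1.8 at a = 20%. The sign can reverse: a = 10%, b = 5% gives (0.025 + 0.015) / 0.55 = 7.3% vs 10.0%, an odds ratio of 0.71 in favour of posoleucel.

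**Masking a real benefit.** If posoleucel halves recurrence in those who clear either way (10% to 5%) and b = 30%, the comparison shows (0.0125 + 0.090) / 0.55 = 18.6% vs 10.0%.

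**In single trials.** Simulating 200,000 trials with a = 10%, the observed rate is higher on posoleucel in about 80% of them when b = 30%, and in about 51% when b = 10%.

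**Information.** At a = 10% and b = 30%, expected recurrences are 22.6 × 0.209 + 10.3 × 0.10 ≈ 4.7 + 1.0 = 5.7, for a model with treatment and three covariates. A fall from 30% on placebo to 10% on posoleucel among about 23 and 10 clearers would have roughly 32% power.

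**The case against.** The strongest objection is that the operative SAP drops this endpoint and all testing. That stands: a reader might infer that the trial's report will contain a misleading recurrence test, and the documents do not support this. What remains is that Section 10.3.1.3 is the only method given for this endpoint, so any later analysis that follows the protocol would use it.

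Second, durability does not rest on recurrence alone. The key secondary endpoint (progression or non-relapse mortality during the study) is analysed in all mITT participants, and freedom from target organ disease at the end of the study is also not limited to clearers. This stands too, but neither endpoint captures return of viremia without organ disease.

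Third, the size comes from assumed recurrence risks, and the true denominator is uncertain. The endpoint does not tie clearance to Day 29, and Appendix 8 defines clearance for recurrence as two consecutive results below 32 copies/mL. This is correct, and it is why a range is shown.

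Fourth, the direction point can be called literal, since the key secondary, also a bad outcome, uses the same phrasing. It is a wording fault to correct and carries no weight in the selection argument.

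Finally, recurrence presupposes clearance, so the restriction is partly a matter of definition. That supports describing recurrence among clearers; it does not support testing it between arms.

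**Conclusion.** The point holds against the protocol plan. A formal between-arm test among clearers conditions on a response to treatment and does not estimate a randomized effect. Under the stated assumptions, with 10% recurrence in those who clear on either arm, the apparent odds ratio runs from 1.0 to 3.2 while treatment has no effect on recurrence.

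A reader might infer that the test would make posoleucel look harmful. That is not established. The bias is zero if both kinds of clearer carry the same risk and favours posoleucel if those who clear only on treatment carry a lower one. The documents do not say which applies. An unknown direction is itself a reason not to test. The SAP's planned outputs are unaffected.

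**What to change.** In Section 10.3.1.3 and the synopsis:

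- Take recurrence among clearers off the list of endpoints tested like the primary. Report counts and percentages by arm, with no between-arm test.
- Add a supportive durable-clearance endpoint in all mITT participants: cleared at the primary endpoint, with no recurrence, target organ disease progression, cross-over or death through Week 24. Analyse it with the primary model, with the alternative that the percentage is greater on posoleucel. Keep it outside the confirmatory sequence.
- State one clearance definition for both, since the Day 29 rule (below LLOQ) and the two-consecutive-results rule in Appendix 8 differ.
- State how missing follow-up is counted. Carry into Section 10.3.1.3 the synopsis rule that counts clearers who cross over as recurrences, or remove it from both places.

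The cost is wording and programming; follow-up through Week 24 is already scheduled. No change to the abbreviated SAP is needed, and an analysis added after the termination should be labelled post hoc.

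The drawback is that durable clearance largely restates the primary effect and has modest power (about 42% to 73% at 41 per arm in the scenarios above). Those figures count only recurrence as failure after clearance; adding progression, cross-over and death would change them. It should be read beside the descriptive recurrence counts.

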#### 10.3.1.4 Cross-Over Analyses

Undetectable viremia (less than LLOQ) at Day 29' of the Cross-Over Period will be summarized by cross-over group using counts and percentages, together with exact (Clopper-Pearson) 95% confidence intervals for the true percentages. Achieving AdV viremia  $< 400$  copies/mL AdV DNA at Day 29' of the Cross-Over Period and AdV disease recurrence during the 24-week Cross-Over Period among participants who had clearance of AdV viremia (after cross-over) will be analyzed in the same way.

The AAUC for plasma AdV viremia ( $\log_{10}$  copies/mL AdV DNA), as assayed by qPCR, through Week 24† of the Cross-Over Period will be summarized by cross-over group using descriptive statistics.

The Kaplan-Meier estimated median time to resolution of AdV viremia will be presented for each cross-over group, together with the 95% confidence interval for the true median. Cross-over participants who do not achieve resolution of AdV viremia will be censored as of their last study visit. The number and percentage of censored and uncensored participants will be presented by cross-over group.

Progression from viremia to target organ disease (for participants without target organ disease at screening, progression of target organ disease (for participants with target organ disease at screening), or non-relapse mortality during the 24-week Cross-Over Period will not be analyzed, because all cross-over participants must have already progressed to target organ disease prior to being crossed over.

#### 10.3.2 Analysis of Safety

Safety will be analyzed and compared between treatment received based on data from the Primary Study Period. In addition, for purposes of complete reporting, safety will be reported for data from the Cross-Over Period by treatment received in the Cross-Over Period, but no comparisons will be made between the two treatments.

The primary safety endpoint is the incidence and severity of TEAEs, including individual AESIs, during the study. The safety profile will be further assessed based on changes in clinical laboratory assessments, vital signs, ECGs, and physical examinations. All safety analyses will be based on the Safety Population.

Safety analyses in general will be descriptive and will be presented by study period (Primary Study Period or Cross-Over Period) and treatment group or cross-over group in a tabular format. Categorical endpoints will be summarized using number and percentage of participants within each category. Continuous endpoints will be summarized descriptively with summary statistics (number of non-missing observations, mean, standard deviation, median, minimum, and maximum).

A TEAE is defined as an adverse event with a start date and time on or after the administration of investigational product or placebo or that worsened in severity after administration of investigational product or placebo through the end of the study. For AEs with a missing start date, the AE will be considered treatment-emergent unless there is additional information indicating that the AE started prior to study treatment. The number and percentage of participants with TEAEs will be tabulated by Medical Dictionary for Regulatory Activities (MedDRA) System Organ Class and Preferred Term for each treatment group/cross-over group. This will be done overall, by severity, and by relationship to treatment. Adverse events leading to discontinuation of the study, SAEs, and AESIs will be summarized by treatment group. By-participant listings will also be provided for any deaths, SAEs, AESIs, and adverse events leading to discontinuation of study drug.

The incidence and severity of acute GVHD during the study, the incidence and severity of chronic GVHD during the study, the incidence and severity of CRS during the study, and the incidence and severity of any treatment-emergent AESIs during the study will each be

summarized by treatment group for the Primary Study Period and by cross-over group for the Cross-Over Period using counts and percentages.

Clinical laboratory data will be summarized by laboratory test, visit, and treatment group using descriptive statistics. The changes from baseline to each post-baseline visit will also be summarized.

Vital signs data will be summarized by visit and treatment group for each vital sign using descriptive statistics. The changes from baseline to each post-baseline visit will also be summarized.

ECG data will be summarized by visit and treatment group for each quantitative ECG parameter using descriptive statistics. The changes from baseline to each post-baseline visit will also be summarized.

Abnormal physical examination findings will be presented in a by-participant data listing.

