## 5 STUDY DESIGN

### 5.1 Overall Design

This is a Phase 3, multicenter, randomized, double-blind, placebo-controlled study to assess the safety and efficacy of posoleucel as compared to placebo for the treatment of AdV infection in pediatric and adult recipients of HCT with AdV infections receiving SoC.

Approximately 82 participants at approximately 50 clinical sites in the US, Europe, and Canada who meet all of the inclusion criteria and none of the exclusion criteria may be enrolled into the study and randomized █ to receive posoleucel or placebo. Randomization will be stratified █

█ It is expected that no more than 30% of participants, but at least 10% of participants, will be  $\geq 18$  years of age.

Enrollment of participants  $<1$  year of age will occur once preliminary safety data are available from 5 participants  $\geq 1$  and  $\leq 6$  years of age. On 16May2023, the DSMB reviewed data from 6 participants aged 1-6 years that have completed through D29 and recommended opening enrollment to patients  $<1$  year of age. An additional meeting will be held once 6 patients  $<1$  year old have been enrolled and completed through D29 of the study.

Posoleucel is to be administered at a fixed cell dose based on weight, as █ sequential infusions separated by █ (see [Section 7.1](#)).

The Primary Study Period is 4 weeks (28 days) for evaluation of efficacy, including the primary endpoint, plus 20 weeks for safety follow-up, for a total study duration of 24 weeks. For participants who cross over, the Cross-Over Period is 4 weeks (28 days), plus 20 weeks for safety follow-up. Participants who experience recurrence and receive an additional dose will have safety follow-up for 20 weeks after the additional dose of study treatment.

At Day 29, all participants will be assessed for the primary endpoint, virologic response.

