### 7.7.1 Permitted Concomitant Therapy

Participants in both treatment arms will continue to receive SoC per their Treating Physician. Any medications, therapies, or procedures performed as SoC will be documented in the appropriate eCRF.

Clinically available (non-investigational) antiviral agents (eg, acyclovir, ganciclovir, foscarnet, maribavir, letermovir) and the use of intravenous immunoglobulin are permitted during the study. For this study, the use of maribavir and letermovir to treat CMV infections will be considered non-investigational, regardless of the regional regulatory approval status.

Cidofovir is not currently approved for the treatment of AdV infection in any regions conducting this trial. Given the unknown efficacy of cidofovir against adenovirus infection and known toxicity (e.g. nephrotoxicity) associated with its use, it is recommended that patients do not initiate or continue the use of cidofovir at the time of enrollment into the study. Cidofovir may be initiated or stopped at any time based on investigator judgment during the study. The dose and regimen of cidofovir is not restricted but must be documented in the EDC as a concomitant medication if used.

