### Assessment of Intensity

The severity of all AEs will be graded according to the Common Terminology Criteria for Adverse Events (CTCAE) version 5.0. For those AE terms not listed in the CTCAE, the following grading system should be used:

- CTCAE Grade 1: Mild; asymptomatic or mild symptoms; clinical or diagnostic observations only; intervention not indicated
- CTCAE Grade 2: Moderate; minimal local or noninvasive intervention indicated; limiting age-appropriate instrumental activities of daily living
- CTCAE Grade 3: Severe or medically significant but not immediately life-threatening; hospitalization or prolongation of hospitalization indicated; disabling; limiting self-care activities of daily living
- CTCAE Grade 4: Life-threatening consequences; urgent intervention indicated
- CTCAE Grade 5: Death related to the AE

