3.5.3 Clinical Laboratory Tests

Clinical laboratory data (hematology, clinical chemistry, and routine urinalysis) from the Primary Study Period will be summarized by laboratory test, visit, and treatment group using descriptive statistics. The changes from baseline to each post-baseline visit will also be summarized.

Listings will be presented for selected laboratory data and the test values outside the normal range will be flagged.

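### Laboratory safety tables pool all ages as plain means and changes by visit, which dilutes a small child's change and gives no by-arm count of participants with a relevant change

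*Protocol*

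**What the plan says.** Protocol 10.3.2 gives the method for laboratory data: "Clinical laboratory data will be summarized by laboratory test, visit, and treatment group using descriptive statistics". It then adds: "The changes from baseline to each post-baseline visit will also be summarized". The statistics for continuous safety data are the number of observations, mean, SD, median, minimum and maximum (Protocol 10.3.2; SAP 3.1 and 3.5).

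SAP 3.5.3 keeps the method: hematology, chemistry and urinalysis results from the Primary Study Period "will be summarized by laboratory test, visit, and treatment group using descriptive statistics", with changes from baseline. It adds one further output: "Listings will be presented for selected laboratory data and the test values outside the normal range will be flagged".

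On age, Protocol 6.1 sets no limit, and Protocol 5.1 expects that "no more than 30% of participants, but at least 10% of participants" will be 18 or older. Section 5.1 also records that the DSMB recommended opening enrollment below 1 year.

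Neither document states any normalisation of laboratory values. That the summaries are in raw units is therefore a reading of plain descriptive statistics; no table shells are given.

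**The concern.** If normal values of an analyte rise with age, as is assumed here for creatinine, the same absolute change is a large relative change in an infant and a small one in an adult. A pooled mean change in original units weights each participant by absolute change. The tables also run visit by visit, so peaks at different visits fall in different rows, and the number of participants who ever had a relevant change cannot be recovered for either arm.

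The documents do otherwise elsewhere. Exclusion criterion 3 reads transaminases and bilirubin as multiples of the upper limit of normal, and Appendix 8 defines hepatitis and its progression by multiples of that limit and by change relative to baseline. SAP 3.3.2 uses pediatric age bands for demographics, and SAP 3.4.2 splits the primary endpoint at 12 years.

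At stake is how clearly liver and kidney safety can be compared between arms when most participants are expected to be children. Kidney function matters because cidofovir may be started or stopped during the study, and Protocol 7.7.1 refers to its "known toxicity (e.g. nephrotoxicity) associated with its use".

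**Working it through.** **Denominator.** Protocol 10.1 gives 82 participants and Protocol 5.2 gives 41 per group. With the protocol's rates of 0.55 and 0.25, two-sided alpha 0.05 and 80% power, n per arm = [1.960 × √(2 × 0.40 × 0.60) + 0.842 × √(0.55 × 0.45 + 0.25 × 0.75)]² / 0.30² = (1.358 + 0.555)² / 0.09 = 40.7, so 41 per arm and 82 in total. The plan's figure is reproduced. It serves here only as the denominator of the arm mean.

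**Assumed values (none is in the documents).** Creatinine in mg/dL: small child 0.2 to 0.4, adolescent 0.6, adult 0.8 to 1.0.

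**One doubling.** Shift of the arm mean = baseline / 41.
- Child: 0.2/41 = 0.005; 0.4/41 = 0.010.
- Adult: 0.8/41 = 0.020; 1.0/41 = 0.024.
- Relative weight of the child: 0.2/1.0 = 0.2 to 0.4/0.8 = 0.5. This ratio does not depend on arm size.

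**Two contrasting arms.**

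| Statistic of change (mg/dL) | Ten children, 0.2 to 0.4 | One adult, +2.0 |
|---|---|---|
| Mean | 10 × 0.2/41 = 0.049 | 1 × 2.0/41 = 0.049 |
| Median (all others unchanged) | 0 | 0 |
| SD | 0.087 | 0.312 |
| Maximum | 0.2 | 2.0 |
| Share at least doubled | 10/41 = 24% | at most 1/41 = 2.4% |

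The SD and maximum separate the two arms, but they make the arm with ten affected children look the milder one. No planned laboratory table shows the last row.

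**Simulation of one arm.** 41 participants and 20,000 runs; adults 10%, 20% or 30%, adolescents 20%, the rest children. Baselines centre on 0.3, 0.6 and 0.85, with 25% variation between participants and 10% or 20% between visits.
- One child doubling: expected shift 0.3/41 = 0.007, against a sampling SD of the mean change of 0.008 to 0.020. It does not stand out.
- Eight children doubling: 8 × 0.3/41 = 0.059, against a sampling SD of 0.010 to 0.022, or about 3 to 6 SDs. It shows.
- Maximum change: a single doubled child sets it in 89% to 95% of runs at 10% variation and in 37% to 53% at 20%.
- Maximum raw value: a single doubled child sets it in about 0.4% to 3% of runs.
- Count at 1.5 times own baseline or more: 1.0, 4.0 and 8.0 for 1, 4 and 8 doublings at 10% variation; about 1.8, 4.5 and 8.1 at 20%.

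**False positives of a ratio count.** At 20% variation, the chance that an unchanged participant reaches 1.5 times baseline at one visit is P(Z ≥ ln 1.5/0.20) = 0.021, or 41 × 0.021 = 0.9 per arm. Taking the worst of the seven post-baseline visits in SAP Appendix 1, Table 2, with independent variation, gives 41 × [1 − (1 − 0.0213)⁷] = 5.7 per arm. At 10% variation both figures are below 0.01.

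**The case against.** The strongest reply is that the laboratory tables are not the main safety instrument. The primary safety endpoint is treatment-emergent adverse events, including those of special interest. Under Appendix 4 a clinically significant laboratory abnormality is an adverse event, and "The severity of all AEs will be graded according to the Common Terminology Criteria for Adverse Events (CTCAE) version 5.0". These events are counted by arm, system organ class, preferred term and severity (Protocol 10.3.2, SAP 3.5.1). GVHD, whose staging uses bilirubin, is tabulated by arm as an event of special interest. The DSMB reviewed data from six children aged 1 to 6 before enrollment below 1 year opened. Cidofovir is available to both arms, and the protocol recommends against starting or continuing it at enrollment. The SAP serves an abbreviated report after termination for futility, so further splits would produce small cells.

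Most of this stands. A reader might infer that pediatric organ toxicity is hidden or cannot be shown, or that adults alone drive the mean. The documents do not support that: the routes above exist, a frequent pediatric effect would move the mean, and dilution of a single case affects adults too. Nor does the median stay at zero unless half the arm changes; that holds only if everyone else is exactly unchanged.

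The other routes are nevertheless incomplete. An abnormal result becomes an adverse event only on the investigator's judgment, and Appendix 4 leaves out findings associated with the underlying disease unless more severe than expected. Adenovirus hepatitis and nephritis are manifestations of the disease under study (Protocol 9.1.2). The listings cover selected tests only, give no by-arm counts, and flag against a normal range that is not said to be age-specific.

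**Conclusion.** The point holds in a limited form. The stated laboratory method suits this age range poorly: a small child's relative change is diluted, and participants with a relevant change are not counted by arm in any laboratory table. A child's doubling carries about 0.2 to 0.5 of an adult's weight in the arm mean. One such case is lost in the mean, while eight in an arm of 41 would be visible.

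These sizes rest on the assumed creatinine values and variation, and on the planned 41 per arm. After early termination the arms may be smaller, which makes each shift larger and the mean less precise but leaves the 0.2 to 0.5 ratio unchanged. Power, type I error and the primary safety endpoint are unaffected. The change is worth making because it is cheap and improves the only by-arm laboratory analysis in the SAP.

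**What to change.** In SAP 3.5.3, and in Protocol 10.3.2 if it is amended, keep the planned summaries and add for creatinine, ALT, AST, bilirubin and blood counts:

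1. By-arm counts of the shift from baseline to worst post-baseline CTCAE v5.0 grade, the scale already used for adverse events.
2. A by-arm summary of each participant's worst ratio to own baseline.
3. Out-of-range flags and multiples of the upper limit based on age- and sex-appropriate reference ranges. The documents do not say that such ranges are held, so confirm this with the central laboratory.

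A split by age, using the SAP 3.3.2 bands or at least the 12-year cut, is optional. The 12-year cut alone still pools infants with 11-year-olds.

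The cost is a few more tables from results already collected, and small cells if age is split. A ratio threshold also brings false positives: about 0.9 per arm for one comparison at 1.5 times baseline with an assumed 20% variation, and more for the worst of several visits. Such counts should be read as a comparison between arms. If the database is already locked, SAP section 1 requires the additions to be documented as deviations in the study report.
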